5.3. Sample Size Considerations

The sample size for the 1st primary endpoint was determined at 120 resulting in approximately 30 subjects to be enrolled in the blinded arm.

The sample size for the 2nd primary endpoint was estimated using the One-Sided Lower-Limit Confidence Intervals for One Proportion approach. Expecting a proportion of 80% with a lower bound of the 95% confidence interval of about 70% the sample size is estimated to be 87.

A sample size of 87 would require approximately 22 subjects to be enrolled in the KODEX guided arm.

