Current clinical studies on the KODEX-EPD occlusion feature have reported on the safe and effective use of the system in standard practice. However, the performance of the KODEX-EPD occlusion feature has not been evaluated using a standardized workflow in a blinded setting in a homogenous patient group. Furthermore, in an effort to minimize therapy, a direct comparison between the success of the freeze when initiating therapy based on the occlusion feature vs the assessment of occlusion by fluoroscopy has not been evaluated. The study design indicates a post-market interventional clinical

investigation to evaluate the endpoints of the study. No follow-up is foreseen ensuring a minimal burden to the subjects participating in the study.

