5. STATISTICAL CONSIDERATION

5.1. Study Endpoints

5.1.1. *Primary Endpoints*

1. The accuracy, sensitivity, specificity and positive and negative predictive values of the KODEX-EPD PV occlusion feature as compared to conventional venographic method of fluoroscopy with contrast dye that will be used to guide the procedure.
2. The success of the freeze when freeze is initiated based on the assessment of the KODEX-EPD PV occlusion feature as compared to the success of the freeze when freeze is initiated based on the assessment with fluoroscopy and contrast dye.

5.1.2. *Secondary Endpoints*

- KODEX-EPD data collection
- Fluoroscopy system data collection
- Fluoroscopy time
- Fluoroscopy dose
- Number of contrast dye injections
- Contrast dye volume
- Time to isolation (TTI)
- Number of ablations per vein
- Procedure time (skin to skin)

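### Section 5.3 sizes primary endpoint 2 from a one-proportion limit for the KODEX guided arm, but the endpoint is a between-arm comparison whose precision is stated nowhere

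*Combined protocol and SAP*

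**What the plan says.** Section 5.1.1 words primary endpoint 2 as the success of KODEX-initiated freezes "as compared to the success of the freeze when freeze is initiated based on the assessment with fluoroscopy and contrast dye". Sections 2.2.2 and the synopsis carry the same endpoint. Section 1.3.3 gives as one reason for the study that "a direct comparison between the success of the freeze when initiating therapy based on the occlusion feature vs the assessment of occlusion by fluoroscopy" is still lacking.

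Section 5.3 states: "The sample size for the 2nd primary endpoint was estimated using the One-Sided Lower-Limit Confidence Intervals for One Proportion approach". It takes an expected proportion of 80% "with a lower bound of the 95% confidence interval of about 70"%; on that basis "the sample size is estimated to be 87". It then assigns the number to one arm: "A sample size of 87 would require approximately 22 subjects to be enrolled in the KODEX guided arm". The blinded arm, which provides the fluoroscopy-initiated freezes, has its own figure of 120 (about 30 subjects), set for endpoint 1.

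Section 2.4 plans 25 guided patients at the Brussels site and at most 20 blinded patients at each of two centers. Section 5.4.1 declares the analysis descriptive and rules out inference. Section 5.4.2.1 plans summaries at the level of the test, the vein and the patient. It describes no between-arm estimate and no interval.

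**The concern.** A sample size is attached to a comparative endpoint, but the method behind it involves one group. It uses no comparator rate, no comparator size, no target difference or margin, and no target width for the difference. The comparator's 120 was chosen for a different question, the diagnostic performance of the occlusion feature. The plan therefore never says how precisely the two guidance methods can be compared.

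What is at stake is how endpoint 2 will be read. Under 5.4.2.1 the report could show two similar percentages, with nothing to indicate how large a true difference they leave open. Because 5.3 presents 87 as the size for this endpoint, a reader may take similar percentages as evidence that the two methods perform alike.

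**Working it through.** **Step 1: reproduce 87.** Inputs from 5.3: expected proportion 0.80, lower limit 0.70, confidence 95%. The exact (Clopper-Pearson) lower limit with 2.5% in the lower tail is L = Beta quantile(0.025; x, n − x + 1), with x = 0.8n. At n = 87, x = 69.6 and n − x + 1 = 18.4, so L = 0.7005. This is the smallest n with L ≥ 0.70, so the plan's figure reproduces. It is the lower limit of a two-sided 95% interval; a one-sided 95% exact limit would need only 64. The one-sided label in 5.3 therefore needs clarifying, but the arithmetic is sound.

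**Step 2: what 87 was derived from.** Only 0.80, 0.70 and the confidence level enter the formula. No quantity from the fluoroscopy-initiated freezes appears.

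**Step 3: numbers available for the comparison.** Section 5.3 does not name the unit. Its own ratios are 87/22 = 3.95 and 120/30 = 4, so about four units per patient is assumed here, with each unit taken as one evaluable freeze. Then 25 guided patients give 100, 22 give 88, 40 blinded patients give 160, and the 20 blinded patients at one center give 80.

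**Step 4: half-width of the difference.** With independent freezes, half-width = 1.96 × √(p₁q₁/n₁ + p₂q₂/n₂), where q = 1 − p. The documents give no fluoroscopy-initiated rate, so equal rates of 80% and 90% are shown as assumptions. For 87 v 120 at 80%: 1.96 × √(0.16/87 + 0.16/120) = 1.96 × 0.0563 = 0.110.

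| Guided v blinded freezes | Basis | 80% in both arms | 90% in both arms |
|---|---|---|---|
| 87 v 120 | figures in 5.3 | ±11.0 points | ±8.3 points |
| 100 v 160 | planned enrolment, 2.4 | ±10.0 | ±7.5 |
| 100 v 80 | 25 guided, 20 blinded at Brussels | ±11.8 | ±8.8 |
| 88 v 80 | 22 guided, 20 blinded at Brussels | ±12.1 | ±9.1 |

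With 80% in the guided arm and 70% or 90% in the blinded arm, 87 v 120 gives ±11.7 or ±10.0.

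**Step 5: clustering within patient.** With four freezes per patient, the variance is multiplied by 1 + 3 × ICC. The documents give no ICC; 0.1 to 0.3 is an assumed range. For 87 v 120 at 80%, 11.0 × √1.3 = 12.6 and 11.0 × √1.9 = 15.2 points. For 100 v 160 the range is 11.4 to 13.8.

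**Step 6: what equal results would leave open.** If both true rates are 80% and freezes are independent, the standard error (SE) is the half-width divided by 1.96. The chance that the 95% interval still includes a 10-point deficit is Φ((half-width − 0.10)/SE):

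- 100 v 160: about 50%
- 87 v 120: about 57%
- 100 v 80: about 62%

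Clustering raises these figures.

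**Context only.** The plan specifies no test. If a two-sided 5% test were applied to a true 70% v 80%, power would be about 37% (87 v 120), 43% (100 v 160) or 35% (100 v 80), using the unpooled variance and independence.

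**The case against.** The strongest reply is section 5.4.1. The study calls itself descriptive and disclaims inference; there is no hypothesis, margin or test for endpoint 2, and nowhere does it claim equivalence or non-inferiority. Sizing a descriptive study on the precision of the new arm's rate is an ordinary choice, and 5.3 openly ties the 87 to the guided arm. This stands as far as it goes: the gap is not a failed power calculation. It does not close the gap, because endpoint 2 remains worded as a comparison and a descriptive comparison still has a precision, which the plan does not give.

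Several stronger readings are tempting, and the documents do not support them:

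- **That 87 is miscalculated.** It is not; it reproduces under an exact limit (Step 1).
- **That 87 has no bearing on the comparison.** It is one of the two sizes that set the width of the difference. The accurate statement is that it was not derived from a comparative target.
- **That the study is underpowered.** No test is planned, so the power figures give scale and nothing more.
- **That equal results would usually leave a 10-point deficit open.** Before clustering the chance is 50% to 62%, close to even at planned enrolment.
- **That ±10 to 12 points is a fixed property of the design.** It depends on rates near 80%, on independence and on four evaluable freezes per patient.

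The denominators are also fairly questioned. Section 2.2.1 says the number of veins and tests varies and removes some data from the primary analysis, which would widen the interval. Ablations per vein are counted separately in 2.2.3, so freezes need not equal veins. The documents do not define freeze success, so any stated precision attaches to an outcome that still needs a definition.

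**Conclusion.** The point holds as a mismatch between an endpoint and its sizing. Section 5.3 offers 87 as the size for endpoint 2, but 87 governs only the precision of the guided-arm rate, and no figure there comes from the comparison that the endpoint names.

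On the stated assumptions, the difference can be estimated to roughly ±10 to 12 points at 80% in both arms, or ±7.5 to 9 at 90%. For the 5.3 figures at 80%, an ICC of 0.1 to 0.3 moves this to ±12.6 to 15.2. The independent-freeze values are the favourable case if outcomes within a patient are positively correlated. All of these describe sampling error only: allocation is not randomized, so an interval would not cover differences between the patients in the two arms.

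**What to change.** 1. In 5.3, state that 87 sets the precision of the guided-arm rate only and was not derived from the between-arm comparison.
2. In 5.3, add the expected 95% half-width of the between-arm difference as a range with its assumptions. With about four evaluable freezes per patient and independent freezes, it is about ±10 to 12 points at 80% in both arms and about ±7.5 to 9 at 90%. For 87 v 120 at 80% with an ICC of 0.1 to 0.3, it is about ±12.6 to 15.2.
3. In 5.4.2.1, report endpoint 2 as the estimated between-arm difference with a 95% confidence interval that accounts for clustering within patient. State that a small or absent difference will not be read as equivalence of the two guidance methods.

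The cost is wording in two sections and slightly more analysis, with no added patients. The drawback is that the stated precision will look less favourable than the present text suggests.

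### Section 5.3 names a one-sided 95% limit for primary endpoint 2, but its 87 matches a two-sided exact limit and carries no allowance for veins clustered within patients

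*Combined protocol and SAP*

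**What the plan says.** Section 5.3 gives the whole basis for the size of the KODEX guided arm in a few lines. It names the method: "The sample size for the 2nd primary endpoint was estimated using the One-Sided Lower-Limit Confidence Intervals for One Proportion approach". The expected proportion is 80%, with a "lower bound of the 95% confidence interval of about 70% the sample size is estimated to be 87". The conversion to patients follows: "A sample size of 87 would require approximately 22 subjects to be enrolled in the KODEX guided arm". For primary endpoint 1 the same section gives only a total, "determined at 120 resulting in approximately 30 subjects to be enrolled in the blinded arm", with no derivation.

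Section 5.3 does not give the interval type (exact, Wilson, Wald), the area in the lower tail, the unit that the 87 counts, or any intra-patient correlation. Section 2.4 plans 25 patients in this arm, not 22. Section 2.2.1 treats every occlusion test and every vein as its own data set and lists reasons for leaving data out of the primary endpoint analysis. Section 5.4.1 makes the analysis descriptive. Section 5.4.2.1 summarises by test, vein and patient but names no method for correlated observations.

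**The concern.** Because no inference is planned, expected precision is the only justification offered for the size of this arm, and it is the only precision target that the plan states for either primary endpoint. A reader should therefore be able to recover 87 from the method named, and to know which bound the trial expects to report. Neither is possible as written. A one-sided 95% limit leaves 5% in the lower tail and a two-sided 95% interval leaves 2.5%; the same 87 observations give different bounds under the two.

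The second issue is independence. Veins treated in one patient share an anatomy, an operator and a procedure, so their outcomes may be correlated. If they are, about four veins from each of about 22 patients carry less information than 87 independent veins, and an interval computed as if they were independent is too narrow.

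**Working it through.** **Inputs.** From 5.3: expected proportion p = 0.80, target lower limit about 0.70, level 95%, n = 87, 22 subjects. From 2.4: 25 patients. Observations per patient: 87/22 = 3.95 and, for endpoint 1, 120/30 = 4, so about 4.

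**Step 1: reproduce 87.** The exact (Clopper-Pearson) lower limit with tail area a is the a-quantile of a Beta(np, n − np + 1) distribution. I look for the smallest n at which it reaches 0.70 when p = 0.80.

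| Lower tail | n just below | Limit | First n | Limit |
|---|---|---|---|---|
| 2.5% (two-sided 95%) | 86 | 0.6999 | **87** | 0.7005 |
| 5% (one-sided 95%) | 63 | 0.6991 | **64** | 0.7000 |

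The plan's 87 is reproduced exactly with 2.5% in the lower tail. Under the one-sided 95% exact limit, 87 observations give 71.6%.

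**Step 2: does another interval type rescue the one-sided label?** As a hand check, the Wald limit needs n = z² × p(1 − p)/0.10². One-sided: 1.645² × 0.16/0.01 = 43.3, so 44. Two-sided: 1.96² × 0.16/0.01 = 61.5, so 62. All types tried:

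| Interval | One-sided 95% | Two-sided 95% |
|---|---|---|
| Wald | 44 | 62 |
| Wald, continuity-corrected | 53 | 72 |
| Jeffreys | 55 | 77 |
| Wilson | 57 | 81 |
| Agresti-Coull | 58 | 83 |
| Exact | 64 | 87 |
| Wilson, continuity-corrected | 67 | 91 |

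No one-sided 95% entry comes near 87. Requiring whole-number successes moves the one-sided values only within 37 to 74.

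**Step 3: conversion to patients.** 87/4 = 21.75, rounded up to 22. This is plain division; no inflation factor is present.

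**Step 4: effect of clustering.** Design effect = 1 + (4 − 1) × ICC, effective n = n / design effect, then the exact limit at 80%. The documents give no ICC, so the range is my assumption. Each cell shows the two-sided 95% lower limit, then the one-sided 95% lower limit.

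| ICC | Design effect | 87 veins: effective n | Limits | 100 veins (25 patients): effective n | Limits |
|---|---|---|---|---|---|
| 0 | 1.00 | 87.0 | 70.05% / 71.6% | 100.0 | 70.8% / 72.3% |
| 0.05 | 1.15 | 75.7 | 69.2% / 70.9% | 87.0 | 70.1% / 71.6% |
| 0.1 | 1.30 | 66.9 | 68.4% / 70.3% | 76.9 | 69.3% / 71.0% |
| 0.2 | 1.60 | 54.4 | 66.9% / 69.0% | 62.5 | 68.0% / 69.9% |
| 0.3 | 1.90 | 45.8 | 65.6% / 67.8% | 52.6 | 66.7% / 68.8% |

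**Step 5: how much correlation 70% tolerates.** Two-sided, 100 veins: 100/87 = 1.149, so ICC up to 0.149/3 = 0.05. One-sided, 100 veins: 100/64 = 1.5625, so ICC up to 0.5625/3 = 0.19. One-sided, 87 veins: 87/64 = 1.359, so ICC up to 0.359/3 = 0.12. Two-sided, 87 veins: essentially none, since 87 is itself the minimum.

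The 100 assumes four analysable veins from each of 25 patients. Exclusions under 2.2.1 would lower every 100-vein figure.

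**The case against.** Several points on the other side are sound.

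- **The mismatch is conservative.** A reader might infer that the arm is too small. The sidedness error does not support that: 87 exceeds the 64 that the named method needs with an exact interval.
- **The origin of 87 is inferred.** Section 5.3 names no interval type. A two-sided continuity-corrected Wilson limit with whole-number successes also first reaches 70% at 87, and a one-sided 99% Wald limit gives 87 but contradicts the stated 95%. The plan's wording, "a lower bound of the 95% confidence interval of about 70" per cent, can be read as the lower end of a two-sided interval. So this is a mislabelled or ambiguous method, and it would be too strong to say that the sponsor miscalculated. That the one-sided 95% label does not yield 87 stands regardless.
- **The effect of clustering is conditional.** A reader might infer that 87 veins cannot deliver 70%. That depends on an ICC that the documents do not give and on which tail is meant. With the one-sided limit that the plan names, 87 veins still hold 70% up to an ICC of about 0.12. The target is also only approximate: 69% is arguably within its meaning, 66% is harder to defend.
- **There is some slack.** Planning 25 patients rather than 22 offsets a modest correlation. The plan does not say that the three extra patients serve this purpose, and exclusions may use them up.
- **The analysis is descriptive.** No success criterion or error rate hangs on the 70% bound. This limits the consequence to the precision claimed; it does not make the stated derivation correct.

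**Conclusion.** The point holds as a disagreement between stated method and stated number, together with an unstated independence assumption. One-sided 95% limits require about 44 to 67 observations, 64 with the exact method; 87 matches the exact limit with 2.5% in the lower tail. The direction is conservative.

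The clustering loss is modest. For 25 patients it takes the two-sided bound from 70.8% to between 70.1% and 66.7%, and the one-sided bound from 72.3% to between 71.6% and 68.8%, for ICC 0.05 to 0.3. These figures rest on an observed 80%, four analysable veins per patient, the exact interval and an assumed ICC. The consequence is a bound that may look somewhat better than the data will support. Type I error is not affected.

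**What to change.** In section 5.3:

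1. Make method and number agree. Either describe 87 as the exact two-sided 95% figure (2.5% in the lower tail, limit 70.05%), or keep the one-sided 95% limit and state that 87 gives 71.6% against a need of 64. Only the sponsor knows which was intended. Name the interval type, the tail area and the unit counted.
2. Restate the expected lower bound for the 25 planned patients, about 100 veins before the exclusions in 2.2.1, with a design effect of 1 + 3 × ICC and the ICC labelled as an assumption. For ICC 0.05 / 0.1 / 0.2 / 0.3 this is about 70.1 / 69.3 / 68.0 / 66.7% (two-sided) or 71.6 / 71.0 / 69.9 / 68.8% (one-sided), noting that both fall if veins are excluded.

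The cost is wording only. The stated bound becomes slightly less favourable, and the restatement does not require more patients or data.

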2.2. Study Design

2.2.1. Study Schematic

[figure not shown]

Figure 3; Study Schematic

The Cryoballoon procedure consists of the isolation and ablation of the pulmonary veins (PVs). The number of PVs and occlusion tests per PV depends on several factors including patient anatomy. Therefore, data from the KODEX-EPD PV Occlusion feature will be evaluated as a separate set of data for each occlusion test and for each pulmonary vein. Data from a PVI where the diameter of the (common) PV ostium > 28mm, or when the threshold for Distance to Shadow (DTS), Distance to Mesh (DTM) or Distance to Ostium (DTO) is exceeded, or when the Achieve catheter is moving during the

injection, there is a double injection or an incorrect timing of the injection, will not be included in the primary endpoint analysis.

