2.4. Number of patients

A maximum of 20 patients per center will be included in the blinded to KODEX arm of the study. An additional 25 patients will be included at UZ Brussel in the KODEX guided arm of the study.

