2.6.2. Intervention

Patient management and treatment decisions are at the discretion of the care team per routine clinical practice. The KODEX-EPD system is an open-platform system however all catheters/leads used during the intervention need to be calibrated prior to the intervention.

2.6.2.1.Clinical Workflow

- 1) Advance the Achieve spiral mapping catheter (Achieve) to the Left Atrium (LA).
- 2) Image the LA with the Achieve by maneuvering the catheter around the LA under different angles.
- 3) Inflate the Cryoballoon (CB) and advance CB to occlude the ostium, make sure the location of the Achieve is maximal 15 mm distal to the CB. Hold this location for 5 seconds.
 - KODEX-EPD System will obtain a "shadow" of the Achieve at the current location this will take approximately 2 seconds.

Please note that there are 2 types of notifications on the KODEX-EPD system that can be shown when obtaining the 'shadow';

- **DTM; When the distance between the Achieve and the Mesh is > 10mm**
- **DTO; When the distance between the Achieve and the Ostium is > 35mm**

It is recommended to reposition the catheter and acquire a new shadow

- 4) Verify occlusion on fluoroscopy (in the blinded arm) or KODEX(in the KODEX guided arm) by selective contrast injection while simultaneously stepping on the KODEX-EPD System's foot pedal/or the injection button in the KODEX-EPD system is pressed to start the occlusion

assessment with the KODEX-EPD System. The occlusion assessment will take approximately 12 seconds. After which the physician should decide to;

- Proceed with CB ablation and move to next PV
- Reposition CB and repeat step 4.

Please note that for a successful occlusion assessment on the KODEX-EPD system it is important that;

- ***The there is no DTM, DTO or DTS (When the distance between the Achieve and the Shadow is > 10mm) notification on the KODEX-EPD system***
- ***The injection on the KODEX-EPD system is synced with the actual injection***
- ***The Injection is done with one shot.***

If occlusion is not indicated when assessing occlusion in the KODEX guided arm it is recommended to reposition the CB and re-assess the occlusion with KODEX. In total 3 consecutive attempts should be made to obtain occlusion on KODEX.

It is recommended to use an auto-injector where 6cc is injected at 2.5ml/sec and the dye/saline ratio is between 50/50 to 100/0.

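### The 87 in Section 5.3 does not fit its one-sided label, its 70% bound assumes about four independent unnamed units per patient, and Section 5.4 plans no interval to report it

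*Combined protocol and SAP*

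**What the plan says.** Section 5.3 sizes the second primary endpoint (success of the freeze) with the "One-Sided Lower-Limit Confidence Intervals for One Proportion approach" and then states: "Expecting a proportion of 80% with a lower bound of the 95% confidence interval of about 70% the sample size is estimated to be 87". It converts this to patients: "A sample size of 87 would require approximately 22 subjects to be enrolled in the KODEX guided arm". For the first endpoint: "The sample size for the 1st primary endpoint was determined at 120 resulting in approximately 30 subjects to be enrolled in the blinded arm". Section 2.4 sets the guided arm slightly higher: "An additional 25 patients will be included".

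Section 5.3 does not say what is being counted. Section 2.2.1 says that "The number of PVs and occlusion tests per PV depends on several factors including patient anatomy", and that the occlusion data will be "evaluated as a separate set of data for each occlusion test and for each pulmonary vein". Section 5.2 builds the primary analysis set from occlusion tests. In the guided arm one vein can contribute several tests (Section 2.6.2): "In total 3 consecutive attempts should be made to obtain occlusion on KODEX".

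For analysis, Section 5.4.1 describes the study as descriptive, disclaims inference, and provides a count and a percentage for categorical variables. Section 5.4.2.1 adds that primary results will be summarised at three levels: test, vein and patient. The only confidence interval mentioned anywhere in the document is the one in Section 5.3.

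**The concern.** The 80%/70%/87 statement is the plan's only claim about precision, and it raises three doubts.

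- **Tail.** A one-sided limit at 95% puts 5% in the tail, whereas the lower end of an ordinary 95% interval puts 2.5% there. These lead to clearly different sample sizes, and the text uses the language of both.
- **Unit and independence.** About four observations come from each patient and enter a single-proportion formula. Veins, tests and freezes in one patient share anatomy, operator and equipment. If their outcomes are correlated, 87 units carry less information than 87 independent ones.
- **Reporting.** The arm is sized by an interval limit that the analysis section does not produce.

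At stake is whether a reader can rely on the stated precision, and whether accuracy, sensitivity, specificity, predictive values and freeze success will be published with any measure of uncertainty.

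**Working it through.** **Inputs from the documents.** Expected proportion 0.80, target lower limit 0.70, 95% level, n = 87, 22 subjects, and 120 units in 30 subjects (all Section 5.3); 25 guided-arm patients (Section 2.4). **Assumed, because not in the documents:** within-patient ICC of 0.1, 0.2 or 0.3, and equal numbers of units per patient.

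**Step 1: reproduce 87.** Find the smallest n whose lower limit reaches 0.70 when the observed proportion is exactly 80% (x = 0.8n). For the exact (Clopper-Pearson) method the limit is the α quantile of Beta(x, n − x + 1).

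| Method | n, 5% tail (one-sided 95%) | n, 2.5% tail (two-sided 95%) |
|---|---|---|
| Wald | 44 | 62 |
| Wald, continuity-corrected | 53 | 72 |
| Wilson | 57 | 81 |
| Agresti-Coull | 58 | 83 |
| Logit | 59 | 83 |
| Clopper-Pearson | 64 | **87** |
| Wilson, continuity-corrected | 67 | 91 |

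The exact 2.5%-tail limit is 0.7005 at n = 87 and 0.6999 at n = 86. The exact 5%-tail limit passes 0.70 at n = 64 (0.6991 at n = 63) and is already 71.6% at n = 87. No one-sided 95% method gives 87.

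**Step 2: units per patient.** 87/22 = 3.95 and 120/30 = 4.0. Four per patient fits veins, but Section 5.2 counts tests and the second endpoint concerns freezes.

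**Step 3: the limit with correlation, at 25 patients.** With m units per patient, effective n = 25m / (1 + (m − 1) × ICC). For m = 4 this is 100, 100/1.3 = 76.9, 100/1.6 = 62.5 and 100/1.9 = 52.6. Exact lower limits at an observed 80%:

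| Units per patient, tail | Independent | ICC 0.1 | ICC 0.2 | ICC 0.3 |
|---|---|---|---|---|
| 4, 2.5% | 70.8% | 69.3% | 68.0% | 66.7% |
| 4, 5% | 72.3% | 71.0% | 69.9% | 68.8% |
| 3, 2.5% | 69.2% | 68.0% | 66.8% | 65.8% |
| 6, 2.5% | 72.7% | 70.8% | 69.2% | 67.7% |

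The 100 units absorb a design effect of 100/87 = 1.15 at the 2.5% tail, so a limit of exactly 70% holds up to an ICC of about 0.15/3 = 0.05. At the 5% tail, 100/64 = 1.56 gives an ICC of about 0.19. The exclusions in Section 2.2.1 would reduce the number of units further.

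**Step 4: does the analysis report the limit?** Section 5.4.1 gives counts and percentages, and Section 5.4.2.1 gives levels of summary. Neither specifies an interval or a method for correlated data. Section 5.5.2 foresees a separate SAP only to record changes to the planned analyses, so it does not promise to fill the gap.

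**Step 5: how much coverage is lost, and does a remedy work?** In simulated beta-binomial data (40,000 sets per setting; 25 patients, four units each, true 80%; ICC 0.1/0.2/0.3):

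- The unadjusted exact 2.5%-tail lower limit covers 97.6/96.3/94.6%, against a nominal 97.5%.
- A two-sided 95% exact interval on the effective sample size covers 96.7/96.3/96.2%.

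For sparse measures I assumed 30 or 40 patients, four tests each, 15% or 30% negative, true value 80% or 90%, and ICC 0 to 0.3. There the effective-sample-size exact interval covers 96.4 to 99.2%. A cluster-robust logit interval cannot be computed in up to 21% of data sets, because the observed proportion is 0% or 100%.

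**The case against.** The strongest reply is that the number is right and only the wording is loose. Section 5.3 attaches no level to its one-sided approach; the 95% belongs to the following sentence. Sizing on the lower end of an ordinary 95% interval can be read into both sentences and gives 87. That reading is fair, and it is why the fault lies in the label and not in the sample size. It does not make the label clear: a reader who takes it at face value gets 44 to 67. The first crossing at 87 also uses a fractional count (0.8 × 87 = 69.6). With whole counts the exact limits are 69.3% at 69/87 and 70.6% at 70/87, so hundredths of a point mean nothing in practice.

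On clustering, every shortfall depends on an assumed ICC, the target is only approximate, and 25 patients exceed the 22 required. At an ICC of 0.1 the limit is still close to 70%, and the coverage loss is small. All of that stands. The margin, however, covers an ICC of only about 0.05 at the tail that reproduces 87.

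On reporting, the study is descriptive, and anyone could derive an exact limit from published counts. That limit would be unadjusted for clustering, and the by-patient summary supplies neither an interval nor an adjustment. A descriptive interval needs no hypothesis test.

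Two further points are fair. The effective-sample-size interval is one option among several and is somewhat conservative. The second endpoint is also worded as a comparison between methods, which a single-proportion interval does not address; that lies outside this point.

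**Conclusion.** The concern holds in all three parts. The figure 87 is correct for the lower limit of a two-sided 95% exact interval and larger than needed under the one-sided label, so the arm is not undersized for the stated method. The bound treats about four units per patient as independent without saying so. At 25 patients and the 2.5% tail, an ICC of 0.1 to 0.3 lowers it from 70.8% to between 69.3% and 66.7%. The unnamed unit matters about as much: with independence, three units per patient give 69.2% and six give 72.7%. These figures rest on an assumed ICC, equal cluster sizes, an observed 80% and no exclusions.

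The practical harm is modest, because no decision depends on 70%. It should still be corrected: it is the plan's only precision statement, and the primary proportions would otherwise be reported with no uncertainty.

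**What to change.** **Section 5.3.** Name the unit (vein, occlusion test or freeze), the interval method and the tail, and reconcile the one-sided label with 87. Restate the expected limit at the planned enrolment as a range over a stated ICC. Possible wording: *With 25 patients and about four [units] each, the expected exact lower limit (2.5% tail) is about 71% if units are independent and about 67 to 69% for a within-patient ICC of 0.1 to 0.3, before exclusions.* If the 5% tail is meant, the figures are about 72% and 69 to 71%.

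**Section 5.4.2.1.** Add descriptive 95% confidence intervals for all primary measures, with the patient as the cluster. Use a small-sample-adjusted method that copes with sparse cells such as specificity and negative predictive value. One option is an exact interval on the effective sample size (Korn-Graubard type, t-adjusted, effective n capped at the actual n). It can still be computed when the observed proportion is 0% or 100%, in which case it uses the unadjusted n.

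**Section 5.4.1.** Replace the sentence disclaiming inference with: *No hypothesis tests are planned; confidence intervals are descriptive.*

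**Cost.** Some wording, a little analysis work and a slightly less favourable stated precision. No extra patients are needed.
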